**Patient Diaries**

The study will include patient diaries to provide dosing instructions, help patients with treatment planning, and track actual doses of study treatment taken by the patient. Information from the diaries may be used for documenting study treatment compliance as well as dosing time relative to PK blood draws.

## 10. Efficacy, Safety Evaluations, Sample Collection and Testing, and Appropriateness of Measurements

Written informed consent must be obtained prior to any study-specific pretreatment evaluations.

Study procedures related to efficacy, safety, and sample collection and testing assessments and their timing are described in the sections below and shown in the Study Schedule ([Attachment 1](#)).

### 10.1. Efficacy Measures

#### 10.1.1. Efficacy Assessments at Baseline and during Study Treatment

Within 21 days before the first dose of study drug, baseline tumor measurement(s) will be performed on each patient. Throughout the study, patients will be evaluated for response according to RECIST 1.1 (Eisenhauer et al. 2009).

A contrast computed tomography (CT) scan or magnetic resonance imaging (MRI) of the brain will be performed at pretreatment and thereafter approximately every 6 weeks  $\pm$  3 days, if a patient had brain metastases at study entry or if clinically indicated.

Computed tomography, including spiral CT, scans and MRI are the preferred methods of measurement.

The method of assessment used at baseline must be used consistently during the course of each patient's evaluation during the study.

Imaging studies required to investigate known disease should be repeated every 6 weeks ( $\pm$  3 days) following the first dose of study therapy, regardless of any treatment delays, until radiographic documentation of PD as defined by RECIST 1.1. CT of the chest and CT or MRI of the abdomen is required at each time point; CT/MRI of the brain must be performed if baseline assessment identified any lesion in this area (or if clinically indicated).

Responses (CR or PR) must be confirmed no fewer than 28 days from the first evidence of response. Thereafter, a responding patient will be followed approximately every 6 weeks ( $\pm$  3 days) until objective progression is observed.

For patients continuing treatment after study completion (continued access period), efficacy assessments (frequency and type of assessments) will be at the discretion of the investigator, based on the standard of care.

Response assessments during the ongoing trial (and related treatment decisions) will be performed by the treating investigator at the site in cooperation with the local radiologist(s).

### **10.1.2. Efficacy Assessments during the Study Period Postdiscontinuation Follow-Up**

Postdiscontinuation follow-up during the study period will be conducted as described in the Study Schedule ([Attachment 1](#)).

For those patients who discontinue study treatment without objectively measured PD, the investigative sites will continue to monitor patients and periodically evaluate tumor response at the same frequency and by the same method used at baseline and throughout the study until the patient has objective disease progression, starts a new anticancer therapy, or until study completion, whichever occurs first. After the patient has objective disease progression or starts a new anticancer therapy, radiologic tests are no longer required and the patient will be followed up approximately every 3 months [ $\pm 7$  days] until the patient's death or overall study completion, whichever comes first.

Response (CR or PR) should be confirmed before the initiation of additional anticancer therapy. However, initiation of new therapy should not be delayed solely to confirm response.

After patients have discontinued study treatment, they may receive additional anticancer therapy at the discretion of the investigator. These postdiscontinuation therapies should be documented on the CRF.

### **10.1.3. Primary Efficacy Measure (Part B only)**

The primary efficacy measure is Progression Free Survival Rate as defined by RECIST 1.1 (Eisenhauer et al. 2009) provided in [Attachment 6](#) at 3 months.

The PFS time is measured from the date of enrollment to the date of objective progression or the date of death due to any cause, whichever is earlier. The censoring is taken in the following order:

- if a patient does not have a complete baseline disease assessment, then the PFS time will be censored at the enrollment date, regardless of whether or not objectively determined disease progression or death has been observed for the patient; otherwise,
- if a patient is not known to have died or have objective progression as of the data inclusion cutoff date for the analysis, the PFS time will be censored at the last complete objective progression-free disease assessment date.

### **10.1.4. Secondary Efficacy Measures**

The following secondary efficacy measures will be collected at the times shown in the Study Schedule ([Attachment 1](#)).

**Overall Survival (OS):** OS duration is measured from the date of enrollment to the date of death from any cause. For each patient who is not known to have died as of the data-inclusion cutoff date for a particular analysis, OS will be censored for that analysis at the last known alive date.

**Objective Response Rate (ORR):** The objective response rate is the percentage of patients with a best response of CR or PR.

**10.1.5. Disease Control Rate (DCR): The proportion of patients achieving a best overall response of SD, PR, or CR. Resource Utilization**

Investigators will be asked to document the use of best supportive care measures, concomitant medications, transfusions, and treatment-related hospitalization days. Such assessments are to be taken throughout the study through the [30]-day short-term postdiscontinuation follow-up visit.

## 10.2. Safety Evaluations

Investigators are responsible for monitoring the safety of patients who have entered this study and for alerting Lilly or its designee to any event that seems unusual, even if this event may be considered an unanticipated benefit to the patient.

The investigator is responsible for the appropriate medical care of patients during the study.

The investigator remains responsible for following, through an appropriate health care option, AEs that are serious, considered related to the study treatment or study procedures, or that caused the patient to discontinue before completing the study. The patient should be followed until the event is resolved or explained. Frequency of follow-up evaluation is left to the discretion of the investigator.

The timing of all safety evaluations is shown in the Study Schedule ([Attachment 1](#)).

[Table JFCU.10.1](#) presents a summary of AE and SAE reporting guidelines. [Table JFCU.10.1](#) also shows which database or system is used to store AE and SAE data.

**Table JFCU.10.1. Adverse Event and Serious Adverse Event Reporting Guidelines**

Period	Types of AEs/SAEs to be Reported	Collection Database	Lilly Safety System
Baseline (pretreatment)	Preexisting conditions	x	
	All AEs	x	
	SAEs related to protocol procedures	x	x
Study treatment period	All AEs	x	
	All SAEs	x	x
30-day short-term postdiscontinuation follow-up	All AEs	x	
	All SAEs	x	x
Long-term postdiscontinuation follow-up	All SAEs related to protocol procedures or study treatment	x	x
Continued access period	All AEs	x	
	All SAEs	x	x
Continued access follow-up	All AEs	x	
	All SAEs	x	x
After the patient is no longer participating in the study (that is, no longer receiving study treatment and no longer in follow-up)	All SAEs related to protocol procedures or study treatment that the investigator becomes aware of		x

Abbreviations: AEs = adverse events; SAEs = serious adverse events.

Note: The investigator remains responsible for following, through an appropriate health care option, AEs that are serious, considered related to the study treatment or procedures, or that caused the patient to discontinue before completing the study. The patient should be followed until the event is resolved or explained.

a For patients who fail screening, only AEs related to protocol procedures are collected in the collection database.

### 10.2.1. Adverse Events

Lilly has standards for reporting AEs that are to be followed regardless of applicable regulatory requirements that may be less stringent. A clinical study AE is any untoward medical event associated with the use of a drug in humans, whether or not it is considered related to that drug.

Lack of drug effect is not an AE in clinical trials, because the purpose of the clinical trial is to establish drug effect.

Any clinically significant findings from electrocardiograms (ECGs), labs, vital sign measurements, or other procedures that result in a diagnosis should be reported to Lilly or its designee.

Cases of pregnancy that occur during maternal or paternal exposures to study treatment should be reported. Data on fetal outcome and breast-feeding are collected for regulatory reporting and drug safety evaluation.

Study site personnel will record the occurrence and nature of each patient's preexisting conditions, including clinically significant signs and symptoms of the disease under treatment in the study.

After the ICF is signed, site personnel will record the occurrence and nature of any AEs and any change in the preexisting condition(s). All AEs related to protocol procedures are reported to Lilly or its designee.

In addition, all AEs occurring after the patient receives the first dose of study treatment must be reported to Lilly or its designee via eCRF.

Investigators will be instructed to report to Lilly or its designee their assessment of the potential relatedness of each AE to protocol procedure or study treatment via eCRF.

The investigator will decide whether he or she interprets the observed AEs as either reasonably possibly related to disease, to the study medication, study procedure, or other concomitant treatment or pathologies. The investigator answers Yes/No to make this assessment in relation to study treatment and study procedure.

Patients will be evaluated for AEs at each visit and will be instructed to call their physician to report any AEs between visits.

The NCI-CTCAE v 4.0 will serve as the reference document for choosing appropriate terminology for, and grading the severity of, all AEs and other symptoms. For AEs without matching terminology within the NCI-CTCAE v 4.0 criteria, the investigator will be responsible for selecting the appropriate system organ class and assessing severity grade based on the intensity of the event.

In addition to collecting the AE verbatim and the CTCAE severity grade, AE verbatim text will also be mapped by Lilly or its designee to corresponding terminology within the Medical Dictionary for Regulatory Activities (MedDRA™) dictionary.

If a patient's dosage is reduced or treatment is discontinued as a result of an AE, study site personnel must clearly report to Lilly or its designee via eCRF the circumstances and data leading to any such dosage reduction or discontinuation of treatment.

#### **10.2.1.1. Serious Adverse Events**

An SAE is any adverse event from this study that results in one of the following outcomes:

- death
- a life-threatening experience (that is, immediate risk of dying)
- persistent or significant disability/incapacity
- initial or prolonged inpatient hospitalization
- congenital anomaly/birth defect
- considered significant by the investigator for any other reason

Important medical events that may not result in death, be life-threatening, or require hospitalization may be considered serious adverse drug events when, based upon appropriate medical judgment, they may jeopardize the patient and may require medical or surgical intervention to prevent one of the outcomes listed in this definition.

Serious adverse event collection begins after the patient has signed informed consent and has received study treatment. If a patient experiences an SAE after signing informed consent, but prior to receiving study treatment, the event will not be reported as serious unless the investigator feels the event may have been caused by a protocol procedure.

Data on SAEs that occur before the end of trial will be stored in the collection database and the Lilly Safety System.

Study site personnel must alert Lilly or its designee of any **serious** adverse event (SAE) within 24 hours of investigator awareness of the event via a sponsor-approved method. If study site personnel contact Lilly or its designee by telephone regarding an SAE, study site personnel must also immediately provide official notification on study-specific SAE forms.

This 24-hour notification requirement refers to the initial SAE information and all follow-up SAE information.

Planned surgeries should not be reported as SAEs unless the underlying medical condition has worsened during the course of the study.

Planned hospitalizations or procedures for preexisting conditions that are already recorded in the patient's medical history at the time of study enrollment should not be considered SAEs. Hospitalization or prolongation of hospitalization without a precipitating clinical AE (for example, for the administration of study treatment or other protocol-required procedure) should not be considered SAEs.

Serious adverse events due to disease progression, including death, should not be reported unless the investigator deems them to be possibly related to the study drugs.

The investigator does not need to actively monitor patients for AEs once the trial has ended, unless provided otherwise in the protocol; however, if an investigator becomes aware of an SAE occurring after the patient's participation in the trial has ended, and the investigator believes that the SAE is related to a protocol procedure or study treatment the investigator should report the SAE to the sponsor, and the SAE will be entered in the Lilly Safety System.

Information on SAEs expected in the study population independent of drug exposure and that will be assessed by the sponsor in aggregate periodically during the course of the trial may be found in the IB.

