In another randomized Phase 3 trial, INSPIRE (I4X-IE-JFCB [JFCB]), 947 patients were planned to be randomly assigned to necitumumab plus pemetrexed - cisplatin (PC+N) versus pemetrexed - cisplatin (PC) as first-line therapy for Stage IV nonsquamous NSCLC (Paz-Ares et al. 2013). Enrollment was halted, following an independent data monitoring committee (IDMC) recommendation, after 633 patients because of safety concerns related to thromboembolism as well as the overall number of deaths from all causes that were unbalanced against the experimental group; the trial continued for patients that had been enrolled. Based on the final analysis, PC+N did not improve the efficacy outcome over PC alone in advanced nonsquamous NSCLC (OS HR 1.01, p=0.96; PFS HR 0.96, p=0.66). The addition of necitumumab resulted in a higher frequency of Grade  $\geq 3$  TEAEs. Grade  $\geq 3$  TEAEs occurring more frequently in the necitumumab arm included skin or subcutaneous disorders (14.1 vs. 0.3%), thromboembolic events (9.5 vs. 6.4%), hypomagnesaemia (7.6 vs. 2.2%), asthenia (6.9 vs. 1.9%), vomiting (6.6 vs. 3.2%), dyspnea (5.3 vs. 2.6%), and diarrhea (4.3 vs. 2.2%). The frequency of study drug related deaths was 4.9% and 2.9% for PC+N and PC, respectively.

Based on these data, the combination of necitumumab plus pemetrexed-cisplatin is not being considered for further development. Of note, no safety signal with regard to thromboembolic or potential thromboembolic events, including fatal events, has been identified for necitumumab in completed clinical trials when administered as monotherapy or in combination with mFOLFOX6 chemotherapy.

The randomized Phase 2 trial, I4X-MC-JFCL (JFCL), compared paclitaxel-carboplatin plus necitumumab versus paclitaxel-carboplatin in the first-line treatment of patients with Stage IV squamous NSCLC. The overall efficacy and safety results were generally consistent with those of SQUIRE. Study I4X-JE-JFCM is a Phase 1b/2 study in Japanese patients with Stage IV squamous NSCLC that compares necitumumab plus gemcitabine-cisplatin versus gemcitabine-cisplatin alone. The trial is monitored by an IDMC and continues as planned.

For more details regarding the necitumumab development program, reference is made to the Investigator Brochure (IB).

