#### **9.3.2.2.3.1.7. Cardiorespiratory Disorders**

An increased frequency of cardiorespiratory arrest or sudden death was observed with necitumumab. Cardiorespiratory arrest or sudden death was reported in the pivotal Study JFCC (SQUIRE) in 2.8% (15/538) of patients treated with necitumumab plus gemcitabine and cisplatin compared to 0.6% (3/541) of patients treated with chemotherapy alone. Twelve of the 15 patients died within 30 days of the last dose of necitumumab and had comorbid conditions, including history of chronic obstructive pulmonary disease (n=7), hypertension (n=5), hypomagnesemia (n=4), and coronary artery disease (n=3). Eleven of the 12 patients had an unwitnessed death.

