### **10.2.3. Safety Monitoring**

The Lilly CRP will monitor safety data throughout the course of the study.

Lilly will review SAEs within time frames mandated by company procedures. The Lilly CRP or designee will, as is appropriate, consult with the functionally independent Global Patient Safety therapeutic area physician or clinical scientist, and review:

- trends in safety data
- laboratory analytes
- adverse events
- If a patient experiences elevated ALT  $>5 \times$  ULN and elevated total bilirubin  $>2 \times$  ULN, clinical and laboratory monitoring should be initiated by the investigator. For patients entering the study with ALT  $>3 \times$  ULN, monitoring should be triggered at ALT  $>2 \times$  baseline.
- Details for hepatic monitoring depend upon the severity and persistence of observed laboratory test abnormalities. To ensure patient safety and comply with regulatory guidance, the investigator is to consult with the Lilly CRP regarding collection of specific recommended clinical information and follow-up laboratory tests. See [Attachment 3](#).

Information on SAEs expected in the study population independent of drug exposure and that will be assessed by Lilly in aggregate periodically during the course of the trial may be found in the IB. In the NSCLC population, the occurrence of fatigue/weakness/asthenia, pain/chest pain, dyspnea, cough, nausea, anorexia/decreased appetite, disease progression, metastasis, hemoptysis, and pleural effusion are reasonably anticipated due to the underlying malignancy.

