5.7.3. Deaths, SAEs, and Other Significant AEs

Reasons for deaths (study disease, AE [any AE, study treatment-related AE], etc.) will be summarized separately for 1) all deaths, 2) death on therapy, 3) deaths within 30 days of discontinuation of study therapy, 4) deaths on therapy or within 30 days of discontinuation of study therapy, and 5) deaths after 30 days of discontinuation of study therapy.

Serious adverse events will be summarized by SOC and PT, by maximum CTCAE grade, and by SOC and PT, and repeated for events deemed by the investigator to be possibly related to study medication. A listing of SAEs will be produced.

In addition, the following analyses will be performed:

- listing of adverse events leading to death
- listing of adverse events leading to study treatment discontinuations
- adverse events leading to study treatment dose modification by SOC and PT

Patients in Part A who experienced a DLT will be listed.

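### The rule that progression-attributed SAEs are not reported conflicts with the all-SAE reporting table, so the all-causality SAE counts can be understated by an unknown amount

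*Protocol*

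**What the plan says.** Protocol 10.2.1.1 contains the exception: "Serious adverse events due to disease progression, including death, should not be reported unless the investigator deems them to be possibly related" (that is, drug-related).

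Other statements on the same subject carry no such exception:

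- Table JFCU.10.1 sends all SAEs to both the collection database and the safety system in the study treatment period, the 30-day follow-up and the continued access period.
- Section 10.2.1.1 itself states "Study site personnel must alert Lilly or its designee of any" serious adverse event within 24 hours. It adds that data on SAEs before the end of trial are stored in both systems.
- Section 10.2.1 requires that "all AEs occurring after the patient receives the first dose of study treatment must be reported to Lilly or its designee via eCRF".
- Section 10.2.3 refers to "Information on SAEs expected in the study population independent of drug exposure and that will be assessed by Lilly in aggregate periodically" during the trial, and 10.2.1.1 says the same. Section 10.2.3 then names events anticipated from the malignancy, among them asthenia, dyspnea, hemoptysis, pleural effusion and disease progression itself.

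On the analysis side, SAP 5.7.3 says "Serious adverse events will be summarized by SOC and PT", with a repeat for possibly related events. The SAP does not say whether SAEs attributed to progression are in these tables.

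**The concern.** The trial is open-label with a single arm. A site that follows the exception decides, case by case and without a comparator, whether a serious event reaches the SAE tables. A site that follows Table JFCU.10.1 reports everything. The same event can therefore be counted at one site and not at another, and a reader of the SAE tables cannot tell which rule produced them.

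Attribution may be difficult here. Section 5.2 reports Grade 3 or higher events in the randomised first-line nonsquamous trial as "asthenia (6.9 vs. 1.9%), vomiting (6.6 vs. 3.2%), dyspnea (5.3 vs. 2.6"%), and asthenia and dyspnea are both on the section 10.2.3 list of events anticipated from the disease. Section 9.3.2.2.3.1.7 describes sudden deaths in the squamous trial, where 12 of the 15 patients died within 30 days of the last necitumumab dose: "Eleven of the 12 patients had an unwitnessed death". These data show that events of this kind can come from drug or disease. They do not show how often sites would misattribute them.

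At stake are the completeness and consistency of the SAE counts. The primary endpoint is not affected.

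**Working it through.** The plan states no expected SAE rate, so there is no figure to reproduce. The main check is to follow two events through both rules.

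**Event 1: Grade 3 dyspnea with hospital admission on treatment, judged due to progression and not drug-related.** The admission makes it an SAE under 10.2.1.1.

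- Under Table JFCU.10.1 it is in both databases and enters the SAE tables (SAP 5.7.3), the SAE line of the overview (SAP 5.7.2.1), the interim SAE data and the aggregate assessment.
- Under the exception it enters none of these as an SAE. Under 10.2.1 it is still an AE for the eCRF with a grade, so it can appear in the TEAE tables (SAP 5.7.2.2). The admission can appear in the hospitalization summary (SAP 5.9).

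**Event 2: death within 30 days of stopping treatment, judged due to progression.**

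- Under Table JFCU.10.1 it is an SAE in both databases.
- Under the exception it is not an SAE. It is still counted among deaths by reason, with study disease as a named reason (SAP 5.7.3; Protocol 12.2.9 plans a similar summary), in the deaths line of the overview (SAP 5.7.2.1), and as a PFS and OS event (SAP 5.6.1 and 5.6.2.3).

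So the two rules give different SAE counts for the same patient. The difference can go only one way, because the exception removes SAEs and never adds them.

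**Size, for illustration only.** Let p be the true proportion of patients with a given SAE and f the share withheld as due to progression. Both are assumed, since neither is in the documents.

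- Reported rate = p × (1 − f)
- Chance of at least one report in n patients = 1 − (1 − p(1 − f))^n

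With n = 15, the safety interim size in Protocol 12.2.10:

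| p | f = 0 | f = 25% | f = 50% |
|---|---|---|---|
| 2% | 26% | 20% | 14% |
| 5% | 54% | 44% | 32% |
| 10% | 79% | 69% | 54% |

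For example, at p = 5% and f = 50%: 1 − 0.975^15 = 0.316, against 1 − 0.95^15 = 0.537 with nothing withheld.

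For SAEs of any kind, an assumed true rate of 20% would be reported as 18% (f = 10%) down to 10% (f = 50%). A true rate of 50% would be reported as 45% down to 25%. These figures concern visibility as an SAE only, since the same event may still be seen as a TEAE.

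**The case against.** The best defence is that there is no conflict. Section 10.2 presents Table JFCU.10.1 as a summary, and 10.2.1.1 also excludes planned surgery and planned hospitalization, which the table does not repeat. On this reading the specific text qualifies the general one, and any event judged possibly drug-related is still reported. That is a reasonable reading. It removes the conflict, however, only by accepting that the all-causality SAE tables are filtered by unblinded attribution, and the SAP does not tell the reader so. The remark in 10.2.1 that lack of drug effect is not an AE does not settle it either, because 10.2.1.1 calls the exempted events serious adverse events.

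The defence is right to limit the point in other respects. A reader might infer any of the following, and the documents support none of them:

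- **That deaths go uncaptured.** The survival row in Attachment 1 is marked only for long-term follow-up, but deaths are tabulated by reason and count in PFS and OS.
- **That withheld events are seen by nobody.** AEs still go on the eCRF, hospitalizations are summarised, and SAP 5.10 has the interim review disposition, AE, laboratory and other data.
- **That the aggregate assessment is defeated.** Its event list is in the Investigator's Brochure, and the examples in 10.2.3 are not stated to be that list. Serious dyspnea or effusion not put down to progression remains reportable.
- **That half the cohort is exposed to the filter because the null 3-month PFS rate is 50%.** PFS progression is radiographic and need not involve a serious event. The interim is timed on 2 cycles (2 × 21 = 42 days), about when the first 6-week scan falls due.
- **That the asthenia and dyspnea ratios (6.9/1.9 = 3.6 and 5.3/2.6 = 2.0) measure misattribution.** They are Grade 3 or higher TEAE rates with a different, first-line regimen.

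**Conclusion.** The reporting rules are inconsistent and should be reconciled. Where sites apply the exception, the all-causality SAE tables, the SAE line of the AE overview, the SAE part of the 15-patient interim and the aggregate assessment can be understated, and the shortfall may vary by site. Its direction is known, but its size is not: it depends on which rule sites follow, the SAE rate and the share attributed to progression, none of which the documents give.

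The flat statement that SAE rates are understated goes too far, because a site following Table JFCU.10.1 would report everything. Mortality, PFS and OS are unaffected. What can be lost is an event's status as an SAE, with its 24-hour notification and its place in the SAE tables. A TEAE entry or hospitalization count does not replace that.

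**What to change.** In Protocol 10.2.1.1, limit the exception to individual submission to the safety system. State that every SAE and every death from first dose through the 30-day follow-up is recorded in the collection database, whatever its attributed cause, and is entered as the medical event rather than as progression. Annotate the safety-system column of Table JFCU.10.1 and qualify the 24-hour notice rule to match.

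In SAP 5.7.3, add a sentence that the SAE tables include events attributed to progression.

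A repeat SAE table excluding those events is optional. It needs one added CRF item, because the Yes/No relatedness answers in 10.2.1 cover study treatment and study procedure only.

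The cost is protocol, SAP and CRF-guideline wording and some extra SAE entries per site. No visits or patients are added.
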